## I SAFETY MONITORING

The study will monitor participant safety. One aspect of this monitoring is to evaluate potential participants at screening to determine whether it is safe for them to participate in the interventions.

### ***I1 Potential Risks***

This study is minimal risk as defined by 45 CFR 46.102: "the probability and magnitude of harm or discomfort anticipated in the research are not greater in and of themselves than those ordinarily encountered in daily life or during the performance of routine physical or psychological examinations or tests". Therefore, we anticipate no psychological, social or legal risks beyond those of participation in minimal-risk research in general.

Participants may find some of the questions in the questionnaire assessments embarrassing. They may be uncomfortable having their height, weight, waist circumference, and blood pressure measured.

A potential risk to study participants is loss of confidentiality.

### ***I2 Surveillance and Reporting Procedures***

This study does not involve a drug intervention, device intervention, or highly invasive data collection procedure. However, recognizing that unanticipated events can occur in the course of any study, even a minimal risk study, the following reporting protocols will apply.

This study will collect the following information for events that occur during the conduct of study activities (i.e., collection of study data or home visits):

- unanticipated (i.e., unexpected) and related adverse events (possibly related or definitely related to study participation) and
- unanticipated problems that may involve risk to participants or study staff, but do not necessarily result in an adverse event (i.e., harm).

These will be monitored using two mechanisms:

1. Events (Possible AEs) observed (e.g., discomfort with measures, elevated blood pressure) by members of the study team (i.e., data collectors or parent educators) will be reported directly to the project coordinator. Team members will report a detailed description of the possible adverse event including the participant ID number, who reported the event to HEALTH staff; who witnessed the event; when, where, how the event occurred; and any action taken in response. The information will be conveyed by email. The project coordinator, in collaboration with the PI will (1) determine if the event qualifies as an AE, (2) follow-up as appropriate, and (3) report AEs in the REDCap database (the following will be reported in the REDCap database for AEs: AE description with

dates, actions taken in response, and event classifications including final status, expectedness, relatedness, and severity) and to the IRB/DSMB (as appropriate).

2. Weight will be annually monitored as mothers are weighed at 12 and 24 months to be sure that weight loss is not excessive. Should a mother lose greater than 15% body weight over a 12 month period a member of the study team or PI will reach out to the participant and administer Eating disorder Screen for Primary care [ESP], a screening for eating disorder. Appropriate referral will be made if the screen is positive. In addition, those that gain over 15% body weight over a 12 month period a member of the study team or PI will reach out to the participant to refer her to her health care professional.

Mothers who become ineligible over the course of the study (i.e., due to pregnancy) will be withdrawn from the study.

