## 2.c HEALTH description

Participants at HEALTH (intervention) sites receive the Foundational curriculum + evidence-based lifestyle change strategies to prevent weight gain and promote weight loss embedded within and delivered as part of home visits. The HEALTH intervention is guided by PAT’s strength-based, solution-focused model and a socio-ecologic approach recognizing the protective and interactive influences on women across multiple levels.

A detailed sample of the curricular materials unique to the HEALTH intervention are included in Appendix A. In addition to the usual care PAT curriculum content, goal setting related to healthy weight, and the importance of parental modeling of healthy eating and physical activity are incorporated throughout the discussion and visit. Content mirrors the structure of the Foundational curriculum described above, but is enhanced to embed lifestyle change as the following example illustrates: 1) rapport building (e.g., reflective questions to get to know the family such as “What did you notice about your child’s development + What did you notice about your families eating?”), 2) development-centered parenting (e.g., comparing and ordering for math skills + healthy portion size), 3) parent-child interaction (e.g., measuring food in appropriate portion size), 4) family well-being (e.g., address needs in family’s physical and emotional environment such as “Who do you think supports your child to be happy and successful? + What could you do at home to make it easier to eat healthier portions?”), and 5) closing/reinforcement and follow-up plans (e.g., feedback on goals, praise for success). Other objectives include skill building and strategies to address: reduction of high-sugar beverages, substituting healthy for unhealthy foods, portion control, and eating patterns. Physical activity goals encourage a total of 150 minutes (2.5 hours) of moderate-intensity exercise (e.g., brisk walking) and/or lifestyle activity per week. HEALTH participants will be provided pedometers, allowing them to track and self-monitor their steps.

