## ***J2 Interim Monitoring and Early Stopping***

Data from the study will be monitored on a continuous basis by the PI and research team. The PI, along with the research team. The PI and all Co-I's and research coordinators will meet every 3 months or as needed to review progress and issues. All serious adverse events (SAEs), adverse events (AEs), and anthropometric values will be reviewed by the investigators on an ongoing basis.

The Data and Safety Monitoring Board (DSMB) will have overall responsibility for monitoring the emerging results. The focus of the DSMB will be on safety issues, recruitment, retention, protocol adherence and data quality and timeliness. The DSMB will meet at least twice each year and more frequently if needed.

We have no outcome-based rules for participant termination (i.e., no participant will be terminated simply based on poor response to the intervention). The only anticipated circumstances under which a participant would be terminated from study participation would be if we, or the NIH or DSMB, determine that it would not be safe for the participant to continue. In addition, per IRB requirement, participants may withdraw from the study early if they decide they are no longer interested in participating.

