### ***K2 Training***

All study team members will receive training in proper conduct of human subjects research. For data collectors conducting screening and measuring outcome data, the study team will conduct training on study procedures. Training will include methods for screening potential participants for eligibility, securing and verifying informed consent, and completing on-site assessments of anthropometrics, blood pressure, and surveys. Depending on the number of families served by the PAT site the previous year, we may hire 1-3 data collectors near each site. To ensure accuracy and appropriate inter-assessor agreement, multiple data collectors hired per site may complete duplicate measures on practice individuals.

Parent educators at sites randomized to HEALTH will also complete human subjects training. They will review materials provided by the Human Research Protection Office and complete the required quizzes, which will be returned to the research coordinator; she will then provide the results to the Human Research Protection Office for inclusion of the parent educator as a study team member.

---

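### I2 collects only a narrow set of adverse events, observed during visits, while J2 and Appendix B assume all adverse events are available for review

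*Combined protocol and SAP*

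**What the plan says.** Section numbers here follow the headings in the body of the protocol, which differ from those in its table of contents.

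- **I2, Surveillance and Reporting Procedures.** Information is collected "for events that occur during the conduct of study activities (i.e., collection of study data or home visits". Two kinds of event qualify. One is "unanticipated (i.e., unexpected) and related adverse events (possibly related or definitely related to study participation". The other is a problem nobody foresaw that could put mothers or staff at risk, whether or not anyone is harmed. There are two mechanisms. In the first, study-team members, named as data collectors or parent educators, pass on possible adverse events that they observe. The coordinator and the principal investigator decide whether each one qualifies, and REDCap records its expectedness, relatedness and severity. In the second, weight is checked at 12 and 24 months for a loss or gain above 15% over 12 months.
- **J2, Interim Monitoring and Early Stopping.** "All serious adverse events (SAEs), adverse events (AEs), and anthropometric values will be reviewed by the investigators on an ongoing basis".
- **Appendix B.** The principal investigator reports on being notified of, or observing, an adverse event. Annual reports summarise any adverse event. The DSMB assesses risk against benefit. No limit on setting, expectedness or relatedness is stated.
- **Table 1.** The only safety row concerns excessive weight loss. No adverse event inquiry is scheduled.
- **2.c, HEALTH description.** "Physical activity goals encourage a total of 150 minutes (2.5 hours) of moderate-intensity exercise" per week, with pedometers supplied.
- **K2, Training.** "Parent educators at sites randomized to HEALTH will also complete human subjects training", which leads to their inclusion as study-team members. No equivalent is stated for usual care educators.

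**The concern.** J2 and Appendix B describe a review of a full stream of adverse events, and I2 does not create one. Its limit on setting matters most. HEALTH aims to change diet and activity in daily life, so harm from it would most naturally arise between visits, and I2 as worded does not collect events there.

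If that stands, investigators and the DSMB would review an incomplete record without a clear statement that it is incomplete. A low count could not support a statement that HEALTH is safe. A difference between arms would also be hard to interpret, because the plan does not establish that educators in the two arms report on the same footing.

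**Working it through.** No stated figure in the plan needs reproducing. The check is a comparison of texts, followed by one illustration of scale.

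**Step 1. Scope, side by side.**

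| Question | I2 | J2 | Appendix B |
|---|---|---|---|
| Setting | Data collection or home visits | No limit | No limit |
| Expectedness | Unexpected only | No limit | No limit |
| Relatedness | Possibly or definitely related | No limit | No limit |
| How events come to light | Observed and passed on; weight check | Not stated | Notification or observation |

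**Step 2. A test case.** A mother in the HEALTH arm is injured on a walk that she took to meet her activity goal. Suppose the injury is unexpected and judged possibly related, so that it passes I2's filter on type. It happened neither at a measurement visit nor at a home visit, so I2 does not collect it, even if it is serious. J2 says it will be reviewed. Appendix B would have it reported if someone told the principal investigator, but nothing in the plan prompts anyone to ask.

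**Step 3. I2 against itself.** If only unexpected and related adverse events are collected, REDCap fields for expectedness and relatedness have little to distinguish beyond possible versus definite. I2 also gives discomfort with measures as an example of a reportable possible event, although I1 lists that discomfort as foreseen. The text therefore does not settle whether the filter acts before reporting or after it.

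**Step 4. Size of the window.** Inputs:
- 23 home visits over two years, the prior-trial average (2.d). The sample schedule of about 13 core and 10 maintenance visits gives the same total.
- Range: 15 and 30 visits (2.d gives the shares of families below 15 and above 30), and 50 visits from the Study Abstract's maximum of 25 per year × 2.
- 3 data-collection visits: baseline, 12 and 24 months (H2).
- Assumptions: each visit falls on its own day, follow-up is 730 days, and events are spread evenly over time.

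Share of days in the window = (home visits + 3) / 730.

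| Home visits | Contact days | Share of 730 days |
|---|---|---|
| 15 | 18 | 2.5% |
| 23 | 26 | 3.6% |
| 30 | 33 | 4.5% |
| 50 | 53 | 7.3% |

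Counted in hours the window is smaller. Usual care home visits are planned at 60 minutes (2.b), and HEALTH is embedded in the same visits. Taking 1 hour for each data visit as well (assumed), 26 h / (730 × 24 = 17,520 h) = 0.15%.

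**Step 5. The two arms.** Data-collector visits and the weight check follow the same schedule in both arms, and HEALTH is not planned to add home visits. The one documented difference is in K2: human subjects training and study-team status are stated for HEALTH educators only, while I2 assigns reporting to study-team members. Whether a usual care educator is a reporter is therefore unclear.

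**The case against.** The strongest reply is that this is a minimal-risk trial with no drug, device or highly invasive procedure. It excludes women who cannot take part in a walking program, and its monitoring plan is described as proportionate. J2's promise can be read as covering all events that are recorded. Appendix B gives a passive route for events notified from outside visits, and the details of DSMB review are left to a charter that is not among the documents. J3 plans no comparison of adverse events between arms. Narrowing J2 would remove the contradiction as well as widening I2 would.

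Part of this stands. The consequence is confined to safety reporting, and the direction of reconciliation is the sponsor's choice. But J2 does not say that it means recorded events only, and a passive route in an appendix does not undo the explicit limit on setting in I2.

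A reader might also infer more than the text supports:

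- **That I2 discards every expected or between-visit event.** It also collects unanticipated problems, lets possible events be forwarded before classification, and has the weight check, which can detect some diet-related harm between visits in both arms.
- **That capture is 9%,** from 23 visit hours against 150 min × 104 weeks / 60 = 260 h of encouraged activity. Visit hours are not a part of exercise hours, and the 150 minutes is a goal rather than achieved activity, so the ratio is not a capture fraction.
- **That HEALTH educators detect events better.** K2 describes human subjects materials and quizzes, not training in event detection. Educators in both arms are asked to record visits and complete checklists.
- **That events are classified by unblinded staff.** The documents do not describe masking of the coordinator or the principal investigator.

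**Conclusion.** The contradiction holds. I2's collection rule is narrower than J2 and Appendix B in setting, expectedness and relatedness, and I2 is unclear about its own filter. Followed literally, it provides no route for events between visits, apart from those that show as a weight change above 15%.

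Under even spread and one visit per day, about 3.6% of follow-up days lie inside the window, and no more than 7.3% at the largest visit count considered. That makes it plausible that most events would be missed, but it does not show it: the documents give no event rate, and mothers may mention events later at a visit.

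Differential capture by arm remains a possibility resting on K2 alone. The primary weight analysis does not depend on any of this. The point is a worthwhile and inexpensive improvement, not a threat to the main result.

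**What to change.** 1. Reconcile I2, J2, K2 and Appendix B. State once which events are collected, in which settings, by whom, and whether expectedness and relatedness are entry criteria or classifications made after reporting. State whether usual care educators are reporters, and put educators in both arms on the same footing.
2. At the existing 12- and 24-month surveys, have the data collector ask every mother in both arms the same short question on injuries, hospital care and other serious health events since the last measurement visit. It can be asked by phone or video under Appendix C.
3. Record the answers whatever their expectedness or relatedness, and list them by arm for the DSMB. Keep spontaneous reports as a separate source, so that the solicited data remain comparable between arms.

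If the sponsor prefers to narrow J2 and Appendix B instead, the plan should say plainly that events between visits are not systematically collected and that low counts will not be read as evidence of safety.

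The cost is one survey item at two existing visits, a few minutes each, and one DSMB table. The drawbacks are recall error over 12 months, some unrelated events to classify, and no coverage of withdrawn mothers after they leave, because 1.f ends their measurement.

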### ***I3 Safety Monitoring Plan***

A Data Safety and Monitoring Board (DSMB) will oversee study implementation. Further details on the Data Safety and Monitoring Plan and the Data Safety Monitoring Board are located in Appendix B.

## **J Statistical Plan**

### ***J1 Sample Size Determination and Power***

We are confident the tabulated computations that led to our decision to randomize 40 sites (20 to each arm) are, if anything, conservative. Tabulations are based on weight at 24 months as the primary outcome and are for two-sided tests at the 0.05 significance level.

**Table 2:** Number of subjects required in each PAT site for two-sided tests at the 0.05 level of significance.

# PAT sites per group	Power	Between group difference	Intraclass correlation coefficient		
			0.01	0.02	0.05
19	0.8	4	6	6	7
	0.9	4	8	8	11

---

The table entries (Table 2, above) are the required sample size per cluster completing data collection for power values of .8 and .9; for ICC values of .01, .02, .and .05; for 19 PAT sites per group, and for between group differences of 4 between-group difference in the baseline to 24-month change in body weight that can be detected. Prior data from the HEALTH effectiveness trial found the standard deviation of the change in weight from baseline to 24 months was 8.3 kg. To be conservative, the computations assume an increased value of 10 for the standard deviation. The computations also assume 7 mother will complete 24 months of follow-up at each of 19 PAT sites. The number actually enrolled will be increased to 10 mothers (to account for a potential dropout rate of 30%) and 40 sites (20 per arm). Based on the above parameter assumptions, Table 3 indicates that to achieve a power of 0.8 with 19 PAT sites per group and an intraclass correlation coefficient as high as 0.05, the between-group difference in the change in weight from baseline to 24 months would have to be 4. Since the HEALTH study saw a 24-month decrease in weight of 1.5 (+/- 8.3) kg in the intervention group and a 24-month increase of 3.2 (+/-7.6) kg in the control, we are confident the target of 19 PAT sites per group with 7 mothers providing 24-month data is sufficient. We emphasize these computations are conservative because they allow for more variability (i.e., assume a larger standard deviation) than was observed in HEALTH, and because our analysis will add power by including data on the dropouts who do not provide 24-month data but who do provide data at 12 months.

## ***J2 Interim Monitoring and Early Stopping***

Data from the study will be monitored on a continuous basis by the PI and research team. The PI, along with the research team. The PI and all Co-I's and research coordinators will meet every 3 months or as needed to review progress and issues. All serious adverse events (SAEs), adverse events (AEs), and anthropometric values will be reviewed by the investigators on an ongoing basis.

The Data and Safety Monitoring Board (DSMB) will have overall responsibility for monitoring the emerging results. The focus of the DSMB will be on safety issues, recruitment, retention, protocol adherence and data quality and timeliness. The DSMB will meet at least twice each year and more frequently if needed.

We have no outcome-based rules for participant termination (i.e., no participant will be terminated simply based on poor response to the intervention). The only anticipated circumstances under which a participant would be terminated from study participation would be if we, or the NIH or DSMB, determine that it would not be safe for the participant to continue. In addition, per IRB requirement, participants may withdraw from the study early if they decide they are no longer interested in participating.

## ***J3 Statistical Methods***

Initial analyses will use t-tests and chi-square tests to compare baseline characteristics across groups. If continuous variables do not satisfy the normality or equal variance assumptions of the t-tests, we will explore data transformations and, if appropriate transformations cannot be identified, may employ Wilcoxon's test.

The primary analysis outcome, weight change between visits, was compared between intervention groups using a linear mixed-effect model with repeated measures. The model included a fixed effect for intervention group, time point, and the intervention

---

by time point interaction with a random effect for participants nested within site. In addition, we may employ models that adjust for covariates (e.g., income), if these are not balanced by randomization. The covariance structure will be determined after evaluating correlation coefficients across time and assessing both Akaike's Information Criterion and Bayesian information Criterion.

Secondary continuous outcomes will be analyzed with the same mixed-effect model. If model assumptions of normality are violated, data will be rank-transformed prior to analysis. The secondary binary outcome will be assessed using a binomial generalized estimating equation (GEE) model repeated measures, while secondary ordinal outcome (physical activity category) will be analyzed using a multinomial GEE model with repeated measures. Due to the multiple comparisons, only the primary endpoint—weight change from baseline to 24 months—will be reported as an unadjusted comparison. All other p-values will be adjusted for multiple comparisons using the Benjamini-Hochberg linear step-up procedure to control the false discovery rate across comparisons. Participants with missing data for all outcomes after baseline were excluded. Participants with at least one follow-up measurement (i.e., 12-month, 24-month, or both) were included in the analyses.

Mixed-effect analyses will also be conducted for subgroups. A per protocol analysis will also be conducted for participants completing at least four home visits. Least squares means with 95% confidence intervals will be report for changes from baseline. No adjustment for multiplicity will be applied to the confidence interval widths.

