### **1.b Participant Recruitment Plans and Consent Process**

Mothers: Our plan to recruit participants mirrors routine PAT ‘rolling’ recruitment throughout the year. Parent educators may provide study fliers or emails to families (parent educators commonly provide materials to families). If the PAT site is hosting an event at which study consent might occur and measures might be taken, parent educators might provide flyers or emails about these events as well. Interested families will either call the number on the flyer or indicate their interest to the parent educator; the parent educator will send the names of mothers who express interest in additional information to the research team who will coordinate an outreach/screening call or text. Screening and data collection procedures will be conducted with a data collector. Data collectors could be a local study team member who calls from (for screening calls) and/or travels from St. Louis (for in person screening and/or measurement) to the site or an individual hired locally to complete data collection. Data collectors will screen potential participants by phone or at site events to ascertain self-reported height and weight, to determine eligibility. If eligible based on self-report, the data collector will consent the participant to a baseline visit and schedule this baseline visit. At the baseline visit, the informed consent process will occur before baseline data collection, with the data collector. These visits may occur in the woman’s home, some other location she prefers (e.g., library, doctor’s office, PAT site), or at PAT site events. As data collection will occur electronically, the participant will have the opportunity to review the consent information on the electronic data collection device (i.e., tablet) before initiating data collection and receive a paper copy of the document, however, we have requested a waiver of documentation of consent. The data collector will also measure height and weight to confirm eligibility based on BMI. Those found to be ineligible and those not providing consent will continue with PAT visits, but will not be part of the study (will not participate in any study measures). To minimize the possibility of coercion or undue influence during the consent process, mothers will have as much time as needed to decide about participation, and the data collector will remind them that their PAT services will not be affected by their decision to participate or not.

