### **1.c Randomization Method**

PAT sites will be randomly assigned to HEALTH or usual care via a dynamic randomization scheme, in which percent of low-income and number of families served will be considered so that we achieve similar distributions in both arms of the study. The first 12 sites will be randomized to HEALTH or usual care arms in a 1:1 ratio within five site pairs where two sites are matched closely on total size and percent of low-income families. There are two sites that cannot be matched; for these two sites, several possible randomizations will be elicited in a 1:1 ratio and the randomization that best maintains the overall balance (on total size and percent of low income families) between the two treatment groups will be selected. Subsequent sites will use a dynamic randomization scheme, the details of which will be determined when those sites are recruited. Again, they will be randomized to best maintain the overall balance (on total size and percent of low-income families) between the two treatment groups.

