### ***L3 Study Timetable***

After initial study set-up (*Table 3*), the collaborative planning phase, IRB approval, and site recruitment and randomization (during August to December 2018), we will begin delivering the HEALTH training curriculum to sites randomized to the HEALTH arm between December 2018 and February 2019. We will begin recruiting mothers in February 2019. With a rolling recruitment, we anticipate recruitment will continue until year 3. This schedule will allow adequate time to finalize analysis, write manuscripts, and disseminate our findings.

Table 3. Study Timeline	Year 1	Year 2	Year 3	Year 4	Year 5
Coordination, collaboration, and planning with PAT National Center	X	X	X	X	X X X X X
Initial site recruitment, data collector training	X				
Parent educators at HEALTH sites receive HEALTH Training Curriculum	X				
Recruitment of families	X	X	X		
Baseline Measurement	X	X	X		
Ongoing HEALTH implementation	X	X	X	X	X
12-month measurement			X X		
24-month measurement				X X X	
Parent educators at Usual Care Sites receive HEALTH Training Curriculum					X
Data analysis, reporting, and dissemination of findings					X X
Sustainability coordination with PAT National Center					X

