#### COVID Procedures and Changes

1. An approved scale, automated blood pressure cuff, and tape measure for assessing waist circumference will be mailed to each site. Once the PAT staff member or data collector has dropped off the scale, blood pressure cuff, and tape measure or the mother is situated in the private room at the PAT site we will either:
  - a. Complete modified data collection via video call, in which we will i) see the participant stand on the scale; ii) use the automated blood pressure cuff; and iii) encircle her waist with the tape measure; these will be recorded entered live in REDCap.
  - b. If the participant is not able to complete a video call, she will complete the data collection by phone, and will receive instructions by the research team on (i) how to take a weight on the scale, (ii) take a photo of weight with her personal device (e.g., phone, ipad), (iii) remove their location tags, and (iv) send a photo of their ID number and weight on the scale, the reading on the blood pressure cuff, and the location on the tape measure to the research team which does not include any identifying factors (e.g. face, location, or name).

For all mothers, we will walk the participant through the process of setting up the scale, using the blood pressure cuff, and using the tape measure (e.g., locating the correct spot for assessing waist circumference). Further, we will utilize their self-reported height to calculate their BMI and ensure eligibility. Weight will be assessed first, as this is used to confirm eligibility. If the mother

is eligible, the remainder of the measures (blood pressure and waist circumference) will be completed.

2. The study team member will then conduct the RedCap Survey through the video call or over the phone.

Once the mother has completed data collection, the PAT staff member or data collector will collect the materials (i.e., scale, automated blood pressure cuff, and tape measure), sanitize them using the wipes provided by the research team, and stored local to the site. If the drop-off method is being used the pickup will ideally be coordinated with planned trips to the home to drop off PAT-related materials (e.g., handouts, materials for activities during personal visits/group connections) or personal visits.

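### The primary weight-change model omits baseline weight, which is measured on every mother; prespecifying it is a free, modest gain in precision and corrects no error

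*Combined protocol and SAP*

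**What the plan says.** Section J3 takes weight change as the primary outcome in a repeated-measures linear mixed model. On the fixed effects it says: "The model included a fixed effect for intervention group, time point, and the intervention", the sentence then continuing to the group-by-time interaction and a random effect for participants within site. The one provision for covariates is: "In addition, we may employ models that adjust for covariates (e.g., income), if these are not balanced by randomization". J3 also states: "Secondary continuous outcomes will be analyzed with the same mixed-effect model", so the same fixed effects carry over to those outcomes.

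Baseline weight is available on everyone. For in-person enrolment, section 1.b says: "The data collector will also measure height and weight to confirm eligibility based on BMI". For remote enrolment, Appendix C says: "Weight will be assessed first, as this is used to confirm eligibility". Table 1 in section H2 also lists weight at baseline, 12 and 24 months.

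On allocation, section 1.c says: "percent of low-income and number of families served will be considered so that we achieve similar distributions in both arms of the study". Weight is not a balancing factor. Section L3 places initial site randomisation in August to December 2018 and then says: "We will begin recruiting mothers in February 2019".

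**The concern.** Subtracting baseline weight fixes the slope of 24-month weight on baseline weight at 1. Adjustment estimates that slope. If the true slope is not 1, change is correlated with baseline weight, and the planned model leaves explainable variance in the residual. The confidence interval is then wider than the data already in hand would allow.

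The same thing can be seen as imbalance. The unadjusted estimate keeps a share (1 − slope) of any baseline difference between arms. Some difference is plausible: only 40 sites are randomised, weight is not balanced, and at the initial sites mothers are recruited after allocation. Subtraction already removes most of it.

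There is also a prespecification issue. J3 first compares baseline characteristics between arms and then allows adjustment for those that look unbalanced. Whether weight enters a model for the primary outcome would therefore be decided after looking at the data, and more than one estimate could be presented.

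**Working it through.** **Inputs from section J1.** Difference 4 kg; two-sided 0.05; k = 19 sites per arm; m = 7 completers per site; ICC 0.01, 0.02, 0.05. On the SD: "To be conservative, the computations assume an increased value of 10 for the standard deviation". The prior trial's value was 8.3 kg.

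**Inputs the documents do not give (assumptions).** The correlation r of 24-month change with baseline weight, taken as 0.1 to 0.4 in absolute value. The ICC is held at the same value after adjustment. For the imbalance calculation, baseline weight is also given ICC 0.05.

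**Step 1: reproduce Table 2, with no adjustment.** With n = 2[SD(z₀.₉₇₅ + z_power)/4]² and m = n(1 − ICC)/(k − n·ICC), rounded up:

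| Power | ICC 0.01 | ICC 0.02 | ICC 0.05 | Printed |
|---|---|---|---|---|
| 0.8 | 5.39 → 6 | 5.64 → 6 | 6.61 → 7 | 6, 6, 7 |
| 0.9 | 7.35 → 8 | 7.86 → 8 | 10.04 → 11 | 8, 8, 11 |

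All six entries agree, and 7/(1 − 0.30) = 10 matches the enrolment target. The sample size takes no credit for baseline adjustment and needs none.

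**Step 2: design point without baseline weight.** SE = √[2 × 10² × (1 + 6 × 0.05)/(19 × 7)] = √(260/133) = 1.398 kg. Power = Φ(4/1.398 − 1.96) = 0.816.

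**Step 3: add baseline weight.** Residual variance is multiplied by (1 − r²), so adjusted SE = 1.398 × √(1 − r²).

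| r | Variance reduction | SE (kg) | 95% CI half-width (kg) | Power, normal | Power, t on 36 df |
|---|---|---|---|---|---|
| 0 | 0% | 1.398 | 2.74 | 0.816 | 0.795 |
| 0.1 | 1% | 1.391 | 2.73 | 0.820 | 0.799 |
| 0.2 | 4% | 1.370 | 2.69 | 0.831 | 0.811 |
| 0.3 | 9% | 1.334 | 2.61 | 0.851 | 0.831 |
| 0.4 | 16% | 1.281 | 2.51 | 0.877 | 0.859 |

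The normal column uses the method that reproduces Table 2. The t column allows for 38 sites. At SD 8.3, SE = 0.83 × 1.398 = 1.160 and unadjusted power is 0.931, rising to 0.934, 0.940, 0.951 and 0.964 for r = 0.1 to 0.4.

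**Step 4: another way to choose r.** If weight has equal variance at baseline and 24 months, r² = (1 − ρ)/2, where ρ is the correlation between the two weights. ρ = 0.95, 0.90, 0.80 and 0.70 give variance reductions of 2.5, 5, 10 and 15% and normal-method power of 0.826, 0.835, 0.854 and 0.873.

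**Step 5: what a chance imbalance leaves behind.** In absolute value, 1 − slope = r × 10/SD_B, where SD_B is the baseline SD. The SE of the baseline difference is SD_B × √(2 × 1.3/133) = 0.1398 × SD_B. For a one-standard-error imbalance the shift is the product, r × 1.398, which is 0.14, 0.28, 0.42 and 0.56 kg for r = 0.1 to 0.4. SD_B cancels.

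**Step 6: simulation.** With 6,000 simulated trials per setting, analysed on site means, both models were essentially unbiased. Type I error was 0.051 and 0.054 for change only, and 0.054 and 0.053 adjusted, at ρ = 0.80 and 0.90. Power rose from 0.818 to 0.851 and from 0.795 to 0.810 respectively.

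**The case against.** The strongest reply is that the gain may be trivial. The planned analysis is valid, the sample size stands, and everything depends on an r the documents do not give. r = 0.4 implies ρ = 1 − 2 × 0.16 = 0.68 under equal variances, so the upper end should not be the headline. At ρ = 0.90 the gain is about 5% of variance and 2 power points. At the hypothesised 4.7 kg and SD 8.3, power is already 0.982 and reaches at most 0.993. This stands, and it is why the point is rated as a recommendation.

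The interval width and the imbalance shift are also not two separate benefits. For chance imbalance, 1.398² − 1.281² = (0.4 × 1.398)² up to rounding, so the shift is the same variance component seen conditionally. That also stands. Nor does Step 5 quantify any systematic difference arising from recruitment after allocation.

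The t-based figures are lower than the normal ones throughout. They show much the same gain, and they show a thin margin: unadjusted power at ICC 0.05 is 0.795, and r = 0.2 brings it to 0.811.

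Three further replies do not remove the point:

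- The covariate clause does not exclude weight. It is optional and data-dependent, however, so it prespecifies nothing.
- J3 might be read as modelling weight at every visit, baseline included, with unconstrained group-by-time terms. With complete data that gives the same estimate as the change score.
- Parts of J3 are in the past tense, which could mean the model was already fitted. J3 also uses the future tense, so this does not show it, but it does bear on timing.

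**Conclusion.** The concern holds as a matter of efficiency and prespecification. Baseline weight is missing from the primary model although it is on hand for every mother. For an assumed r of 0.1 to 0.4, including it reduces residual variance by 1 to 16%, the standard error from 1.398 kg to 1.391–1.281 kg, and raises power from 0.816 to 0.820–0.877. A one-standard-error chance imbalance would move the unadjusted estimate by 0.14 to 0.56 kg, against a design effect of 4 kg. If r is zero there is neither gain nor loss.

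These sizes rest on the assumed r, on the ICC being unchanged by adjustment and, for the imbalance figure, on baseline weight having ICC 0.05. Confidence in the size is medium; the omission itself is plain from the text. Adjusting for weight would not remove recruitment differences in other factors.

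**What to change.** In section J3, prespecify the primary model as follows:

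- Response: change from baseline in weight (or weight itself) at months 12 and 24.
- Fixed effects: group, time, group by time, baseline weight, and baseline weight by time.
- Random effect for participants within site, and choice of covariance structure: as already planned.
- Primary estimate: HEALTH minus usual care, difference in least-squares means at month 24.

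Give each continuous secondary outcome its own baseline value in the same way, and say whether that baseline enters raw or ranked when the response is rank-transformed. Keep any adjustment triggered by observed imbalance, such as income, as a sensitivity analysis only.

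The cost is SAP wording. No data collection or sample size changes, and no analysed mother is lost, because a change score already requires the baseline weight. The change should be made and dated before outcomes are examined by arm.
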